9.4 Access to Individual Subject Treatment Assignments

Stage 1 and Stage 2 will be open-label. Treatment assignments will be known to all personnel involved in the study.

9.5 Interim Safety Analysis and Early Stopping Guidelines

The principal investigators, medical monitor and sponsor will be responsible for reviewing the ongoing safety and laboratory data, and making decisions regarding dose de-escalation and dose stopping in accordance with the rules set out in Section 6.3 for Stage 1. Other than the safety evaluation required to determine whether to proceed to Stage 2 of accrual, no planned formal interim analysis will be performed.

If concerns arise during any data reviews, the sponsor may request additional specific safety data be collected and recommend modifying study conduct.

The sponsor may also terminate the study at any time for reasons which may or may not be related to safety or study conduct.

9.5.1 General Approach/Considerations

A Statistical Analysis Plan (SAP) will be finalized prior to database lock and will include more details of analysis populations and summary strategies. Any changes from the statistical analyses described in this document will be described in the SAP, and any deviation from the final SAP will be described in the final clinical study report.

Safety, Efficacy, and PK assessments will be summarized separately for Stage 1 and Stage 2. Additional summaries and analyses of pooled Phase 1 and 2 data may also be generated based on applicability of dosing regimens.

Descriptive statistics will be provided for selected demographic, safety, and efficacy, and exploratory endpoints by treatment group and time as appropriate. Descriptive statistics on continuous data will include means, medians, standard deviations and ranges, while categorical data will be summarized using frequency counts and percentages. Graphical summaries of selected endpoints may also be presented. For any variable, unless specified otherwise, baseline is defined as the last assessment prior to the first dose of study specified treatment.

9.5.2 Analysis of Key Study Endpoints

9.5.2.1 Adverse Events

Each reported adverse event will be assigned a System Organ Class (SOC), a higher level group term, a high level term and a preferred term according to the current version of the Medical Dictionary for Drug Regulatory Activities (MedDRA). The severity of adverse events will be assigned in accordance with the NCI CTCAE version 4.03 guidelines.

All adverse events will be listed by subject. The subject incidence rate of adverse events occurring between informed consent and first dose of study drug will be summarized by system organ class and preferred term for the Safety Analysis Set.

The incidence rate of treatment emergent adverse events, defined as all adverse events reported as new or worsened after the start of study drug, will be summarized by treatment group, system organ class, preferred term and maximum severity (where appropriate) for all adverse events, serious adverse events, adverse events leading to discontinuation of study specified treatment, adverse events leading to discontinuation from the study and fatal adverse events using subjects in the safety population. In addition, summaries of exposure adjusted adverse event rates may also be presented. These summary tables will also be repeated for treatment related adverse events. The number and percent of subjects reporting adverse events (all, serious, and related) will be tabulated by dose levels. Narratives of all serious and fatal adverse events will also be provided.

A listing and summary of the incidence of dose limiting toxicities present will be reviewed to make dose escalation decisions in Stage 1 review (dose limiting toxicity assessment set) will also be produced by treatment group and by subject.

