5.4 Subject Replacement

Subjects in Stage 1 who are enrolled but not treated and subjects who discontinue treatment before completion of Cycle 1 for reasons other than the occurrence of a DLT may be replaced. Any replacement subject will be enrolled into the same dosing group as that for the subject who withdrew.

Subjects in Stage 2 who are enrolled but not treated will be replaced.

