- BSA Calculation - The body surface area will be calculated using either the Dubois or Mosteller formulas (Appendix D) if the subject is assigned to receive RX-0201, and the calculations will be documented in the subject's medical record and eCRF. The formula used must be the same for the subject throughout the study.
- Resting vital signs: pulse, respiration rate, blood pressure (i.e., after the subject has been seated for at least 5 minutes) and temperature measurements.
- Laboratory tests (for analyte description see Appendix C)
 - Hematology panel
 - Chemistry panel
 - Coagulation tests (Cycles 1 – 16 only)
 - Urinalysis (Cycles 1 – 16 only)
 - Urine pregnancy test (if applicable, Cycle 1 only)
 - Blood collection for biomarker analysis (Cycle 1 only)
- Tumor biopsy (optional- Stage 2 subjects)
- Collection of archived tumor tissue within 4 weeks after initiation of treatment (Stage 2 subjects)

7.5.2 Everolimus Dosing Cycles 1 to n, Days 1 - 21 - Stage 2

Everolimus (10 mg) will be taken orally on Cycle 1 Day 1 at the clinic. Doses after Cycle 1 Day 1 will be taken by the subject at home at approximately the same time every day and consistently with or without food.

7.5.3 RX-0201 Dosing – Cycles 1 to n, Day 1 - Stage 2

Subjects in Stage 2 that were randomized to the everolimus only arm will not receive RX-0201.

RX-0201 will be prepared based upon body surface area and the assigned dose for subjects in Stage 1 or Stage 2 assigned to the everolimus/ RX-0201 treatment arm. All dosing calculations will be documented in the subject's medical record and eCRF (see Appendix D for details). The bag containing RX-0201 will be connected to the infusion pump and the start time recorded when the pump is turned on.

7.5.4 Cycles 1 to n, Day 8 - Stage 2

- Recording of concomitant medication(s). The assessment may be completed by phone for subjects previously randomized to the everolimus alone arm.
- Recording of adverse event(s). Serious adverse events will be reported immediately. Any adverse event that is considered related to study drug(s) will be followed to resolution or return to baseline. The assessment may be completed by phone for subjects previously randomized to the everolimus alone arm.
- Resting vital signs: pulse, respiration rate, blood pressure (i.e., after the subject has been seated for at least 5 minutes) and temperature measurements. (Cycles 1 – 16 only). The

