8.1.2 Serious Adverse Events

A serious adverse event is defined as an untoward medical occurrence that results in any of the following outcomes:

- Death (i.e., all deaths occurring between signing of the consent form to within 30 days after last study drug administration), including deaths due to disease progression. Deaths that occur as a result of an adverse event that started during the study period should be reported. The reported adverse event should be the event that caused the death. Death is the outcome of this serious adverse event.
- Life-threatening situation (i.e., with an immediate risk of death from the event as it occurred but not including an event that, had it occurred in a more serious form, might have caused death).
- In-patient hospitalization or prolongation of existing hospitalization. Of note, an untoward medical occurrence that occurs during hospitalization is an adverse event but a complication that prolongs hospitalization is a serious adverse event. In-patient hospitalization comprises formal admission to a hospital for medical reasons, for any length of time, whether or not hospitalization extends overnight. However, hospital admissions for administration of the study drug, procedures required by the study protocol, or tumor-related diagnostic procedures are not considered serious.
- Persistent or significant disability/incapacity.
- Congenital anomaly/birth defect in the offspring of a subject who received the study drug.
- Other medically significant event. Such events may not be immediately life-threatening or result in death or hospitalization, but based upon appropriate medical and scientific judgment, may jeopardize the subject or may require medical or surgical intervention to prevent one of the outcomes listed above. Examples of such events might include:
 - Allergic bronchospasm requiring intensive treatment in an emergency room or at home
 - New cancers or blood dyscrasias
 - Convulsions that do not result in hospitalization
 - Development of drug dependency or drug abuse

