9.2.2 Analysis Populations

Data from stages 1 and 2 of this study will be combined for both safety and efficacy analyses when appropriate. The following definitions of the various analysis sets to be used will therefore be applied to subjects in Stage 1 and Stage 2 of the study.

Safety Analysis Set:

The safety analysis set includes all subjects who receive at least one dose of study drug(s) with subjects analyzed according to the treatment received. All safety data will be analyzed in accordance with this analysis set.

Full Analysis Set:

The Full Analysis set includes all enrolled or randomized subjects with subjects analyzed according to the treatment assigned at enrollment/randomization. All efficacy endpoints will be analyzed using the Full Analysis set.

Per Protocol Analysis Set:

The Per-Protocol Analysis set will include all subjects without pre-specified major protocol deviations. Sensitivity analyses of some efficacy endpoints may be performed using the per-protocol analysis set.

Evaluable for Tumor Response Analysis Set (Stage 2 only):

The tumor response analysis set will include all subjects in the Full Analysis Set (and Per-Protocol Set if applicable) with a uni-dimensional measurable lesion at baseline (as per RECIST ver. 1.1).

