### **7.2.3 Safety Analysis Set**

The safety analysis set includes all subjects who receive at least one dose of study drug(s) with subjects analyzed according to the treatment received. All safety data will be analyzed in accordance with this analysis set. The safety analysis set will be defined as all subjects who receive at least 1 dose of study drug. These subjects will be analyzed according to the treatment received. All safety data will be analyzed in the safety analysis set.

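### The consent-to-first-dose adverse event table is run on dosed subjects only, so an enrolled subject whose pre-dose event prevents dosing drops out of the one incidence table for that window

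*Protocol*

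**What the plan says.** Protocol 9.5.2.1 plans two kinds of adverse event incidence summary. One covers the period before treatment: events between "informed consent and first dose of study drug will be summarized by system organ class and preferred term for the Safety Analysis Set". The others cover treatment-emergent events, "defined as all adverse events reported as new or worsened after the start of study drug", together with counts of all, serious and related events by dose level.

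Protocol 9.2.2 restricts the Safety Analysis Set to subjects with at least one dose and adds: "All safety data will be analyzed in accordance with this analysis set". SAP 7.2.3 agrees: "The safety analysis set will be defined as all subjects who receive at least 1 dose of study drug". SAP 7.3.5 repeats that safety measures are summarised on this set.

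The protocol expects some subjects to be enrolled and never dosed. Section 5.3 allows up to 5 days from enrollment to dosing, and section 5.4 states: "Subjects in Stage 2 who are enrolled but not treated will be replaced". Protocol 8.1.2 treats as serious "all deaths occurring between signing of the consent form to within 30 days after last study drug administration".

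SAP 8.10 has no consent-to-first-dose table, although SAP 11 records no changes to the protocol.

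**The concern.** The table describes what happens before the first dose, but membership of its population is settled by what happens afterwards. If the event is the reason for not dosing, the event itself removes the subject. That is selection on a consequence of the outcome, and it acts most strongly on the worst events.

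At stake is an accurate account of harm between consent and treatment. In Stage 2 this period can include an optional tumor biopsy within 5 days before Day 1 (Protocol 7.5.1 and Appendix B). Replacement makes the gap hard to see: the dosed count still reaches its target, and nothing in the table shows that anyone is missing.

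**Working it through.** The documents give no figure to reproduce. The check is a comparison of definitions, followed by a small illustration.

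**1. Who can be in the table.** The event window closes at first dose (Protocol 9.5.2.1). The population requires at least one dose (Protocol 9.2.2, SAP 7.2.3). A subject whose pre-dose event prevents dosing has zero doses and is outside the set, so is counted in neither numerator nor denominator.

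**2. Whether another adverse event table recovers the event.**
- The treatment-emergent tables (Protocol 9.5.2.1, SAP 8.10) start after the start of study drug.
- The counts of all, serious and related events are by dose level and fall under the all-safety-data rule in Protocol 9.2.2, so they too need a dose.
- The SAP 8.10 denominator is subjects dosed with RX-0201.

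None covers the window for an undosed subject.

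**3. What lies outside the incidence tables.**
- Protocol 9.5.2.1 lists all adverse events by subject and promises narratives for all serious and fatal events. Neither statement is limited to dosed subjects.
- SAP 7 puts all eCRF data in listings, and SAP 8.11 lists deaths on study.
- Protocol 9.5.3.1 and SAP 8.1 tabulate reasons for discontinuation.

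**4. Direction and illustration.** Let *n* be dosed subjects, *x* of them with a pre-dose event, and *k* enrolled subjects not dosed because of such an event.
- Table as planned: *x/n*.
- Table on all enrolled subjects: (*x* + *k*)/(*n* + *k*).
- Difference: *k*(*n* − *x*)/[*n*(*n* + *k*)], which is never negative.

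Take *n* = 20, the planned upper number for the combination arm in Stage 2, and assume *x* = 0. The values of *k* are also assumed, because the documents give none.

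| *k* | As planned | All enrolled |
|---|---|---|
| 1 | 0/20 = 0% | 1/21 = 4.8% |
| 2 | 0/20 = 0% | 2/22 = 9.1% |
| 3 | 0/20 = 0% | 3/23 = 13.0% |

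Enrolled subjects left undosed for other reasons, without an event, would enlarge the all-enrolled denominator and lower these percentages. The *k* events would still be absent from the planned table.

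**The case against.** The strongest reply is that the worst events are the ones reported individually. A death or serious complication before dosing should reach the by-subject listing and a narrative, and a withdrawal can appear among the discontinuation reasons. This stands, and it limits the point to the incidence table. A reader might infer that these events vanish from the report altogether; the documents do not support that. The SAP is not fully consistent here: SAP 7.3.5 names the Safety Analysis Set for disposition, while SAP 8.1 puts screen failures in the disposition table. The unnumbered Safety Analyses text after SAP 8.6 defines final safety summaries and listings by RX-0201 dosing.

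A second reply is that pre-dose data may be sparse. This also stands. Reporting from consent is explicit only for deaths (Protocol 8.1.2). Protocol 8.1.1 counts procedure complications during study drug administration and follow-up, whereas SAP 8.10 adds screening. Routine questioning follows the start of study drug (Protocol 8.2.1), and Appendices A and B show no adverse event assessment at screening. So it cannot be assumed that every pre-dose event is already collected.

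A third reply is that a dosed safety set is conventional. That is right for treatment-emergent events, and those tables need no change.

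It would also be tempting to read 4.8% as the true rate of biopsy harm. The counts are assumed, and biopsy is optional, so that rate would need the number biopsied as its denominator. Neither the planned table nor the corrected one estimates it.

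**Conclusion.** The point holds for the one table. By the stated definitions, the only adverse event incidence table for the period from consent to first dose excludes every enrolled subject whose event prevented dosing, and so leans toward milder events. This rests on the definitions alone and needs no assumed rate.

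How much it matters in practice is unknown, because the documents do not say how many subjects are enrolled and never dosed, or why. The practical weight is modest. The study is small, open-label and descriptive for safety. Events before any dose say nothing about the safety of the combination, and no dose-limiting toxicity, progression-free survival or response result uses this table. The absence of the table from SAP 8.10, with no change declared in SAP 11, is a related inconsistency: Protocol 9.5.1 requires changes to the planned analyses to be described in the SAP.

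**What to change.** - In Protocol 9.5.2.1, replace *for the Safety Analysis Set* in the pre-dose sentence with *for all enrolled subjects (Full Analysis Set), with enrolled-but-never-dosed subjects shown in a separate column*.
- Add this table to SAP 8.10.
- Add *except the pre-dose AE summary* to the all-safety-data sentence in Protocol 9.2.2 and SAP 7.2.3 and to the denominator statement in SAP 8.10. SAP 7.3.5 needs the same exception.
- Keep the Safety Analysis Set for all treatment-emergent tables.
- List serious events and deaths in consented screen failures where reported. SAP 8.1, which confines screen failures to the disposition table and enrollment listing, then needs a matching exception.

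The Full Analysis Set already exists, and enrolled subjects have a subject number and an assigned treatment. A table on everyone who consented would be wider, but the documents do not show that adverse event data exist for screen failures: a subject number requires completed eligibility documents (Protocol 5.2), and the screening log holds only limited information (Protocol 4.1). The price is that the Full Analysis Set still misses a subject who fails screening because of an event, hence the listing.

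The cost is one small table and a few exception clauses. The differing text on when adverse event collection starts (Protocol 8.1.1 against SAP 8.10) must also be reconciled, because the table can show only what is collected.

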9.5.2.2 Laboratory Safety Data

All hematology, chemistry, coagulation and urinalysis will be listed by treatment group and subject. Where normal ranges are available, values outside of the range will be flagged. The data will be summarized by treatment group using standard descriptive statistics at each of the scheduled time point in the study. For continuous parameters, a summary of the changes from baseline to each post dose laboratory assessment will also be produced for each treatment group.

Shift analysis for selected laboratory parameters between baseline and both the final visit worst-case on-study value will be summarized according to NCI CTCAE version 4.03 toxicity grades.

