9.2.1.2 Secondary Endpoints

- Pharmacokinetics profile of RX-0201 (Stage 1)
- Incidence of adverse events, changes in clinical laboratory tests and vital signs over time (Stage 1 and Stage 2)
- Tumor response, duration of response, time to response, and response rates (Stage 2)

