### Secondary Endpoints:

- Pharmacokinetic profile of RX-0201 (Stage 1)
- Incidence of adverse events, changes in clinical laboratory tests and vital signs over time (Stage 1 and Stage 2)
- Tumor response rate, duration of response, time to response and response rates (Stage 2)

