## Safety Analyses

The incidence of subjects with adverse events and clinical laboratory abnormalities, defined as dose limiting toxicities after 1 cycle of therapy, is one of the primary endpoints. The safety of RX-0201 will be evaluated through reporting using the grading system in the CTCAE version 4.03 for adverse events and laboratory abnormalities. This will be used to grade changes in vital signs, and laboratory assessments to include serum chemistry, hematology, coagulation tests and urinalysis. All statistical methods for safety data will be descriptive in nature.

Dose Limiting Toxicities that occur during Cycle 1 will be tabulated by DLT criteria and RX-0201 dose level. Vital signs will be tabulated and presented as raw data and change from baseline at each time point. Laboratory safety data will be tabulated in shift tables based on laboratory-specific normal ranges. Adverse events will be tabulated by body system, intensity and relationship to study drug.

Vital signs, weight, and data will be summarized using appropriate descriptive statistics, by treatment group and time.

All subjects who receive at least 1 dose of RX-0201 will be included in the final summaries and listings of safety data. All safety analyses will be performed by dose level, treatment cycle, and week, where appropriate.

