### **8.13 Clinical Laboratory Evaluations**

Abnormal laboratory values will be assessed according to NCI CTCAE v4.03 where possible. The criteria for “clinically significant” laboratory abnormalities include a laboratory abnormality that leads to a DLT or a laboratory abnormality that results in any treatment-emergent therapeutic intervention (i.e., concomitant medication or therapy), or any other laboratory abnormality judged by the investigator to be of other particular clinical relevance.

All relevant clinical laboratory tests will be classified as Low, Normal, and High, or Normal/Abnormal according to the normal ranges. This categorical data will be summarized in shift tables comparing the results at each scheduled post-baseline visit with those at the baseline visit.

When there are multiple values within a visit for a particular laboratory variable, the worst value will be taken (worst being the smallest value for criteria below a certain threshold or the largest value for criteria above a certain threshold). If a subject has both a value below the threshold and a value above the threshold, the value furthest from the threshold will be chosen.

Urinalysis data will be presented in subject listings only.

All laboratory (hematology, coagulation, clinical chemistry, and urinalysis) parameters, values, units, normal range, flags collected (normal/abnormal) in the clinical database will be included in by-subject listings for further medical review. Laboratory values with associated CTCAE version 4 grades will have the associated grade displayed.

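### The SAP's laboratory section omits, without declaring it, the protocol's change-from-baseline summary and CTCAE-grade shift, so falls within normal and worsening within Low reach no specified laboratory table

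*Protocol*

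**What the plan says.** Protocol 9.5.2.2 plans four laboratory outputs:

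- listings with out-of-range values flagged;
- by-visit summaries: "The data will be summarized by treatment group using standard descriptive statistics at each of the scheduled time point in the study";
- change from baseline: "For continuous parameters, a summary of the changes from baseline to each post dose laboratory assessment will also be produced for each treatment group";
- a shift analysis of selected parameters from baseline to the final and worst on-study value (the sentence lacks a conjunction, but this is its evident sense), which "will be summarized according to NCI CTCAE version 4.03 toxicity grades".

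These serve a secondary endpoint of both stages. Protocol 9.2.1.2 names "changes in clinical laboratory tests and vital signs over time", and SAP 4.2 and 8.8 repeat it.

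The SAP's Safety Analyses overview says: "Laboratory safety data will be tabulated in shift tables based on laboratory-specific normal ranges". SAP 8.13 says that tests "will be classified as Low, Normal, and High, or Normal/Abnormal according to the normal ranges", and then: "This categorical data will be summarized in shift tables comparing the results at each scheduled post-baseline visit with those at the baseline visit". Individual values, with CTCAE grades where they exist, go into by-subject listings. Urinalysis is listed only.

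For vital signs, the overview and SAP 8.14.2 both keep change from baseline at each time point. Protocol 9.5.1 requires changes to the planned analyses to be described in the SAP. SAP section 11 reports none.

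**The concern.** The secondary endpoint is change in laboratory tests over time. A summary of change from baseline measures that directly, whereas a normal-range shift table records only whether a limit was crossed. Two kinds of deterioration leave no trace in such a table: a fall that stays within normal, and worsening in a subject who is already Low.

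Hematology is where the documents give most reason to look. Protocol 2.3.1 reports lower red-cell parameters in all treated rat groups, persisting through recovery, and decreased red cells in monkeys. Protocol 2.3.2 lists thrombocytopenia (8.7%), decreased platelet count (7.7%) and decreased hemoglobin (5.8%) among the commonest RX-0201-related events when the drug was given with gemcitabine. It lists thrombocytopenia again for the combination in this trial's Phase 1b portion. Worsening within Low is a practical possibility, because the exclusion criteria admit subjects with hemoglobin down to 9 g/dL.

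**Working it through.** **Side-by-side comparison.**

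| Laboratory output | Protocol 9.5.2.2 | SAP laboratory text |
|---|---|---|
| By-subject listings | Yes | Yes |
| Descriptive statistics by visit | Yes | Not specified |
| Change from baseline, continuous parameters | Yes | Not specified |
| CTCAE-grade shift to final and worst value | Yes, selected parameters | Not specified; grades shown in listings |
| Normal-range shift by visit | Not specified | Yes |

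**What each table can show.**

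- Fall within normal: Normal to Normal in the SAP's table. It would usually be Grade 0 to Grade 0 in a grade shift as well, so restoring the grade shift alone does not recover it. The change summary does.
- Worsening within Low: Low to Low in the SAP's table. A grade shift shows it when a grade boundary is crossed, and the change summary reflects it in the group mean.

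**Largest single fall that the normal-range table can hide.** With limits L and U it is (U - L)/U. The documents give no reference ranges, so assume a platelet L of 150 x10^9/L:

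- U = 300: 150/300 = 50%
- U = 400: 250/400 = 62.5%
- U = 450: 300/450 = 67%

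**Illustration of the group-level loss.** The only input from the documents is n = 20 (combination arm, Protocol 3.3). All the others are assumed: normally distributed baseline platelets restricted to 150-450, lower limit 150, normally distributed change with SD 60, one post-baseline visit.

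- Mean change: 95% half-width = t(0.975, 19) x 60/sqrt(20) = 2.093 x 13.42 = 28.1. The probability that the interval excludes zero comes from the noncentral t with noncentrality (fall/60) x sqrt(20).
- Shift count: simulate the probability of Normal to Low with no mean change, and take the smallest count out of 20 whose binomial false-positive probability is at most 5%. With baseline mean 280 that probability is about 0.06 and the cut-off is 4 or more. With baseline mean 230 it is about 0.12 and the cut-off is 6 or more. Then find the probability of reaching the cut-off under the fall.

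| Baseline mean (SD) | Mean fall | Shift count detects | Mean change detects |
|---|---|---|---|
| 280 (70) | 30 | 0.20 | 0.565 |
| 280 (70) | 50 | 0.45 | 0.94 |
| 280 (70) | 100 | 0.96 | >0.99 |
| 230 (60) | 50 | 0.62 | 0.94 |
| 230 (60) | 75 | 0.92 | >0.99 |
| 230 (60) | 100 | 0.99 | >0.99 |

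At baseline 280 and a fall of 50, the Normal-to-Low probability is 0.17. That is 3.4 of 20 subjects, against 1.2 of 20 from within-subject variation alone.

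**The case against.** The strongest reply is that nothing has been removed. Four parts of it deserve an answer.

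- **General format.** SAP 7.3.5 gives n, mean, SD, median and range for continuous variables and applies this to safety measures. The Safety Analyses overview also has a sentence summarizing vital signs, weight and an unqualified data item by treatment group and time, where a word may be missing. A reader might infer from SAP 8.13 that laboratory values get no numeric summary at all. These two sentences mean that the inference goes too far. Neither, however, names laboratory values or a laboratory change from baseline, so neither restores the protocol's analysis.
- **No declared removal.** Because SAP section 11 reports no change, the protocol's analysis formally still stands. SAP section 13, as available, shows only figures, so a table list may exist elsewhere. To say that the analysis was dropped is therefore more than the documents support. What stands is an unreconciled omission from the document that sets the analysis specifications.
- **Other outputs.** Adverse-event tables by maximum severity would show falls reported as events, and every value is listed. That is correct, and it limits the gap to unreported falls. Listings still do not summarize change over time.
- **Selective background.** The percentages above come from the gemcitabine combination, and Protocol 2.3.2 says no significant events in Phase 1b were attributed to RX-0201 alone. They are a reason to examine hematology, not evidence of an RX-0201 effect in this trial.

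**Conclusion.** The point holds as an undeclared mismatch between protocol and SAP on a descriptive secondary safety endpoint. The SAP specifies a coarser laboratory analysis than the protocol and does not say so. It rests on the text alone and needs no assumed figure.

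The size is not fixed by the documents. One might infer that categorizing discards most of the information on a fall. That is not established: the loss is large for modest falls (0.20 against 0.565, or 0.45 against 0.94) and nearly vanishes for large ones (0.96 or 0.99 against above 0.99). These figures depend on assumed platelet distributions and a single visit. They also use a detection rule that neither document plans, since the SAP makes all safety methods descriptive. The primary endpoints are unaffected.

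**What to change.** In SAP 8.13, before database lock:

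1. Add by-visit summaries (n, mean, SD, median, range) of hematology, chemistry and coagulation values, and of their change from baseline, by treatment group at each scheduled post-baseline visit.
2. Restore the CTCAE version 4.03 grade shift from baseline to the final and the worst on-study value, for named parameters, alongside the normal-range shift tables.

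If the sponsor prefers the present SAP analysis, state the change and the reason for it in SAP section 11, as Protocol 9.5.1 requires.

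The cost is a short addition to the SAP and a few standard tables. The data are already collected, and no visit or sample is added.
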